## **4.2 Registration and randomization procedures**

### *4.2.1 General Guidelines for DF/HCC and DF/PCC Institutions*

Institutions will register eligible participants with the DF/HCC Quality Assurance Office for Clinical Trials (QACT) central registration system.

An investigator will confirm eligibility criteria and a member of the study team will complete the QACT protocol-specific eligibility checklist.

### *4.2.2 Registration Process for DF/HCC and DF/PCC Institutions*

The QACT registration staff is accessible on Monday through Friday, from 8:00 AM to 5:00 PM Eastern Standard Time.

The registration procedures are as follows:

- Obtain written informed consent from the participant prior to the performance of any protocol specific procedures or assessments.
- Complete the QACT protocol-specific eligibility checklist using the eligibility assessment documented in the participant's medical record and/or research chart. To be eligible for registration to the protocol, the participant must meet all inclusion and exclusion criterion as described in the protocol and reflected on the eligibility checklist.
- Fax the eligibility checklist(s) and all pages of the consent form(s) to the QACT at [contact].
- The QACT Registrar will (a) review the eligibility checklist, (b) register the participant on the protocol, and (c) randomize the participant when applicable.
- An email confirmation of the registration and/or randomization will be sent to the Overall PI, study coordinator(s) from the Lead Site, treating investigator and registering person immediately following the registration and/or randomization.

### *4.2.3 General Guidelines for Other Investigative Sites: Not applicable*

### *4.2.4 Registration Process for Other Investigative Sites: Not applicable*

## **5 Study Design and Methods**

### **5.1 Design/ Study Type**

The proposed project will proceed in two phases. During phase 1, we will conduct a prospective pilot study assessing the feasibility and preliminary efficacy of the intervention in improving patients' sexual function, QOL, and mood (quantitative objectives). During phase 2, we will conduct qualitative interviews with patients who completed the intervention to explore their perceptions of its acceptability, content, and efficacy, and the optimal timing for its delivery during their survivorship course (qualitative objective).

## **5.2 Study Procedures:**

We will recruit 53 patients with hematologic malignancies 3 months after allogeneic HCT who report having sexual dysfunction causing distress for this study. Once written informed consent is obtained, patients will receive an outpatient multimodal sexual dysfunction intervention. The interventionist will rescreen the patients at the beginning of their initial visit. If patients no longer experience sexual dysfunction before their initial study visit, they will be considered ineligible for the study as they are no longer experiencing distress relating to sexual dysfunction. Because these patients have already signed consent, they will count towards accrual, but will no longer be eligible to participate in the intervention.

Prior to patients' enrollment on this study, we will train a total of two transplant clinicians regarding how to assess and address sexual dysfunction in the transplant clinic. [name] is the Director of the MGH Cancer Center Sexual Health Clinic and a world-renowned expert on sexual dysfunction in cancer survivors. He will first provide transplant clinicians with reading materials regarding how to assess and address sexual dysfunction. The transplant clinicians will review this literature prior to their didactic training sessions with [name]. [name] will then conduct two training sessions with the same two transplant clinicians prior to study enrollment to ensure they acquire the necessary skills to implement the sexual dysfunction intervention in the transplant clinic. One transplant MD and one experienced transplant nurse practitioner (NP) will be responsible for implementing the intervention in the transplant clinic.

[name] will first conduct a two-hour didactic training session with the transplant clinicians, focusing on the following areas:

1) How to perform a comprehensive sexual function assessment: This includes a comprehensive assessment of prior and current sexual history with an emphasis on identifying the causes of sexual dysfunction. [name] will review the sexual function questionnaires that he utilizes in the Sexual Health Clinic to identify causes of sexual dysfunction. These questionnaires will be completed by all study participants at baseline and will be available to the transplant clinicians to review prior to seeing the patients for an intervention visit. [name] will review how to assess various aspects of sexual function including libido, pleasure, orgasm/ejaculation, vaginal symptoms (for women), painful intercourse, erectile and ejaculatory function, premature menopausal symptoms, signs and symptoms of hormonal deficiencies, and psychological barriers to intimacy including body-image issues, self-confidence, anxiety, depression.

2) Normalization of the topic and patient empowerment and education: [name] will also train transplant clinicians regarding the optimal ways to discuss this sensitive topic. He will review strategies to normalize the topic, create a comfortable environment for patients to ask questions, and empower them to become an active part of addressing their sexual health needs. [name] will focus on the language he utilizes in his clinic when speaking to patients regarding their sexual function.

3) Therapeutic interventions for sexual dysfunction in men and women: [name] will also outline therapeutic strategies to address the various causes of sexual dysfunction in men and women. For full details regarding these interventions, please see section 5.5 (therapeutic interventions).

4) When to refer patients for additional expertise: [name] will teach transplant clinicians to identify patients with more complex sexual dysfunction needs including suspected psychological etiology for sexual dysfunction, relationship or intimacy problems, and women with significant vaginal symptoms requiring a vaginal examination.

## Sexual Dysfunction Intervention Post-Bone Marrow Transplant Protocol version 7/02-28-2017

[name] will then conduct an additional 1-hour didactic session with the transplant clinicians. This additional training session will involve case presentations to augment the clinicians' understanding of the various causes and treatments of sexual dysfunction.

Finally, the transplant clinicians will also attend two sexual health clinic sessions with [name] to obtain clinical experience in evaluating and treating patients with sexual dysfunction.

### 5.3 *Selection of study instruments*

#### • **Demographics:**

Patients will complete a demographic questionnaire at baseline detailing their age, sex, race, ethnicity, religion, relationship status (FC will specify their relationship with patients), educational level, annual household income, and living situation [appendix A].

- **Participant-reported measures:** We will administer the following questionnaires at baseline and 6 months after enrollment:
- **Male sexual function:** We will utilize the PROMIS Sexual Function and Satisfaction measures for men including the following domains: Global satisfaction with sex life, interest in sexual activity, erectile function, and orgasm [Appendix B].
- **Female sexual function:** We will utilize the Female Sexual Function Index (FSFI), which identifies problems with sexual desire and interest, sexual arousal, lubrication, reaching orgasm, pain with intercourse, and emotional closeness during sexual activity [Appendix C].
- **Patient-QOL:** We will use the Functional assessment of Cancer Therapy-Bone Marrow Transplant (FACT-BMT) to assess QOL, which has been validated for use in patients undergoing HCT [Appendix D].
- **Mood:** We will use the Hospital Anxiety and Depression Scale (HADS) to assess symptoms of psychological distress (depression and anxiety) [Appendix E], and the PHQ-9 to assess major depressive syndrome [Appendix F].
- **Qualitative Data Collection:** We will also conduct qualitative interviews with approximately 8 male and 8 female patients from the phase I participant pool to participate in the second phase. Participants must complete the 6-month post intervention assessment in phase I prior to enrolling in phase II. We will use a semi-structured interview guide to 1) explore patients' perception of the acceptability and content of the sexual dysfunction intervention; 2) explore patients' perception of the efficacy; and 3) identify the optimal timing of intervention delivery during the survivorship course. We will audi-record the interviews, transcribe them by Audio Transcription Center in Boston, MA, and code and analyze them using NVivo 10 software.

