In this project, we will develop and evaluate the efficacy of a multimodal sexual dysfunction intervention for allogeneic HCT survivors. The proposed project will proceed in two phases. During phase 1, we will conduct a prospective pilot study assessing the feasibility and preliminary efficacy of the intervention in improving patients' sexual function, QOL, and mood. During phase 2, we will conduct qualitative interviews with patients who completed the intervention to explore their perceptions of its acceptability, content, and efficacy, and the optimal timing for its delivery during their survivorship course. Data from this work will help inform a large-scale randomized study of a sexual dysfunction intervention for allogeneic HCT survivors.

The proposed project will assess an innovative and sexual dysfunction intervention that has the potential to substantially enhance the care of survivors of hematologic malignancies. Moreover, such an intervention can be adapted for use with other cancer survivors struggling with sexual dysfunction after their treatment. By implementing a multimodal intervention to improve sexual function, we aim to enhance the QOL, mood, and intimacy of cancer survivors.

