### **3 Research Subject Selection**

#### **3.1 Study Subject Selection:**

We will recruit 53 allogeneic HCT survivors who are at least 3 months post-HCT and without evidence of disease from Massachusetts General Hospital bone marrow transplant clinic to participate in this prospective pilot study.

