## 7 Statistical Analysis

### 7.1 Primary and secondary endpoints:

7.1.1 *Primary endpoint:* The primary endpoint of the proposed study is feasibility. We chose the sample size for this study based on the feasibility of completing the project during the proposed timeframe. The proposed intervention will be deemed feasible if it meets the following criteria:

- At least 75% (95% confidence interval +/- 12%) of patients screening positive for sexual dysfunction causing distress agree to participate in the study and attend the first scheduled intervention visit.
- At least 80% of participants (95% confidence interval +/- 11%) attend at least two intervention visits (either in the transplant clinic or specialty referral).

7.1.2 *Secondary endpoint:* The following secondary endpoints represent the preliminary efficacy endpoints

1. Change in sexual function from baseline to 6 months
2. Change in QOL from baseline to 6 months
3. Change in psychological distress scores (HADs and PHQ-9) from baseline to 6 months
4. To qualitatively 1) explore patients' perception of the acceptability and content of the sexual dysfunction intervention; 2) explore patients' perception of the efficacy; and 3) identify the optimal timing of intervention delivery during the survivorship course.

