## 7.2 ***Sample Size Calculation:***

As stated in section 7.1.1, the primary endpoint of the proposed study is feasibility. We chose the sample size for this study based on the feasibility of completing the project during the proposed timeframe. The proposed intervention will be deemed feasible if it meets the following criteria:

- At least 75% (95% confidence interval +/- 12%) of patients screening positive for sexual dysfunction causing distress agree to participate in the study and attend the first scheduled intervention visit.
- At least 80% (95% confidence interval +/- 11%) of participants who attend the first visit will also attend at least one additional follow-up visit and/or specialty referral.

These estimates are informed by our prior supportive care trial in HCT patients. We are currently conducting a study evaluating a palliative care intervention for patients undergoing HCT. In this study, we have successfully enrolled 40/44 (90.9%) of potentially eligible participants. Only one participant withdrew and did not complete the longitudinal follow-up (2.5%). Given the sensitive nature of the topic, we are making a conservative estimate of feasibility that 60% (0.75 X 0.80) of patients screening positive for sexual dysfunction will attend the first scheduled intervention visit and at least one additional follow-up and/or specialty referral visit.

We will also select approximately 8 male and 8 female patients from the phase I participant pool to participate in the qualitative phase of this study. We chose approximately 8 male and 8 female patients for the qualitative study to ensure that we have sufficient number of patients to achieve thematic saturation. Additionally, we will purposefully select participants with varying times from their HCT to capture participants throughout the survivorship trajectory. Therefore, we will select approximately 5-6 participants who enrolled in the study within each of the following timeframes: 1) less than one year after HCT; 2) greater than one year, but less than two years after HCT; and 3) more than two years after HCT.

7.3 ***Stratification factors and intervention allocation plan for randomized studies:*** not applicable

7.4 ***Definition of an allowance in design for unevaluable/ineligible participants:*** No applicable

7.5 ***Analysis Plan:***

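### Acceptability interviews select on retention: participants who stopped attending or did not return the 6-month forms are excluded or not sought, so the findings carry completer bias

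*Combined protocol and SAP*

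**What the plan says.** Four places in the protocol describe who is interviewed, and they do not agree.

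- Section 1.1 (Overview) plans "qualitative interviews with patients who completed the intervention".
- Section 5.1 repeats this: "we will conduct qualitative interviews with patients who completed the intervention to explore their perceptions of its acceptability".
- Section 5.3 (Qualitative Data Collection) does not mention completing the intervention. It requires the 6-month forms: "Participants must complete the 6-month post intervention assessment in phase I prior to enrolling in phase II".
- Section 7.2 states neither condition: "We will also select approximately 8 male and 8 female patients from the phase I participant pool". Its spread is by sex and by time since transplant: "we will purposefully select participants with varying times from their HCT to capture participants throughout the survivorship trajectory", with about 5 to 6 interviewees in each of three time bands.

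The first interview aim in section 5.3 is to "explore patients' perception of the acceptability and content of the sexual dysfunction intervention". The other aims are perceived efficacy and timing.

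Completion is not defined. Section 5.5 allows up to two transplant-clinic visits plus any sexual health clinic visits, and schedules everyone for a 4-week follow-up, a referral or both. Attendance, response and dropout are not sampling factors anywhere. Reasons are recorded for missed questionnaires (sections 5.4 and 5.7.1) and for clinicians' objections to approaching a patient (section 4.1). No rule records why a participant stops attending visits.

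**The concern.** Stopping the intervention is one of the clearer signs that a participant did not find it acceptable. Choosing interviewees by completion, or by return of the 6-month forms, therefore selects on something close to what the interviews are meant to learn. The likely direction of the bias is favourable.

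The second feasibility criterion counts attendance at a second visit. If it is missed, the trial can report the miss but has no planned source for the reasons. The stated purpose of the pilot is to inform a large randomized study, and that design would need those reasons.

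**Working it through.** **1. The plan's own figures.** Inputs: n = 53 (section 3.1: "We will recruit 53 allogeneic HCT survivors") and planned rates of 75% and 80% with half-widths of 12 and 11 points (sections 7.1.1 and 7.2). The first reads "At least 75% (95% confidence interval +/- 12%) of patients screening positive for sexual dysfunction causing distress agree to participate in the study". The Wald half-width is 1.96 × √(p(1 − p)/n).

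- p = 0.75: 1.96 × √(0.75 × 0.25/53) = 0.117, stated as 12%.
- p = 0.80: 1.96 × √(0.80 × 0.20/53) = 0.108, stated as 11%.
- Joint rate: 0.75 × 0.80 = 0.60, as stated in section 7.2.

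The figures reproduce, so the 80% rate and n = 53 are used below. There is no stated figure for the interview phase beyond about 16 interviewees.

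**2. How many attend only once.** 0.20 × 53 = 10.6, or about 11. This assumes that all 53 attend the first visit. Section 5.2 counts towards accrual consented patients who prove ineligible at rescreening, so the true base may be smaller.

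**3. Size of the interview pool under the two readings.** The plan gives no 6-month non-return rate for this study, so a range is assumed, with non-return taken as independent of attendance. Completion is taken to mean at least two visits (assumption).

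| 6-month forms missing | Two visits and forms: 53 × 0.80 × (1 − m) | Forms only: 53 × (1 − m) |
|---|---|---|
| 0% | 42 | 53 |
| 2.5% | 41 | 52 |
| 10% | 38 | 48 |
| 20% | 34 | 42 |
| 30% | 30 | 37 |

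Either pool easily supplies 16 interviews. The issue is therefore who is in the pool, not how many. If low attenders return forms less often, which is plausible, the forms-only pool also tilts towards attenders.

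**4. What a few interviews with low attenders would add.** For a barrier held by a share π of these patients, the chance that at least one of k independent interviewees holds it is 1 − (1 − π)^k. With k = 4:

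- π = 0.20: 1 − 0.80⁴ = 0.59
- π = 0.40: 1 − 0.60⁴ = 0.87
- π = 0.60: 1 − 0.40⁴ = 0.97

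**5. What it would cost among completers.** For a theme held by 25% of completers (assumption):

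- 16 interviews: 1 − 0.75¹⁶ = 0.990
- 12 interviews: 1 − 0.75¹² = 0.968

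**The case against.** A reader might infer that patients who found the intervention unacceptable cannot be heard at all. The documents do not support that. Disliking the intervention is not the same as leaving it. Patients without improvement at the follow-up visit are referred onward and remain in the study (sections 5.5 and 5.7.2), and a dissatisfied patient who stays and returns the forms is eligible. Under section 5.3 alone, so is a one-visit patient who returns the forms. Section 5.4 gives that assessment to all participants, with remote or paper completion and two reminders. Exclusion by attendance rests only on the undefined completion wording in sections 1.1 and 5.1. For the same reason, the present chance of hearing such a barrier cannot be put at zero. It is unknown, because low attenders may qualify and those who stay may share the barrier.

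A reader might also infer that the primary endpoint is compromised. It is not: both criteria are attendance proportions, non-attenders count in them, and the interviews do not enter the decision.

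Two further points are fair. Views on content and efficacy call for some exposure to the intervention. Having the questionnaire precede the interview also plausibly keeps the interview from colouring the 6-month self-report, although the protocol gives no reason for the order. Both can be respected in the fix.

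What remains is that the interviewee descriptions conflict, one key term is undefined, and on no reading does the plan seek out those who left.

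**Conclusion.** The point holds as completer bias. Participants who did not return the 6-month forms are excluded by section 5.3. Those who stopped attending are excluded under sections 1.1 and 5.1 if completion means a second visit, and are otherwise eligible but unsought. The acceptability findings would probably lean favourable by an amount the documents do not allow one to estimate, and a miss on the second-visit criterion would go unexplained.

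About 11 of 53 participants are affected through attendance at the planned rate, plus an unknown number through missing forms. The gain from four interviews, 59% to 97%, depends on the assumed 20% to 60% prevalence, on independent interviewees and on actually obtaining all four. The matching loss among completers is about 2 points, from 99% to 97%. No planned estimate or feasibility decision is invalidated, so this is a cheap improvement and not a flaw that undermines the trial.

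**What to change.** - Delete the completion condition in both section 1.1 and section 5.1. Amending only one would leave a contradiction.
- Replace the section 5.3 entry rule with: *participants who attended at least the first intervention visit and who have either returned the 6-month questionnaires or passed the end of the 6-month window (plus 2 weeks) without returning them*. This secures exposure to the intervention, and the interview never precedes the questionnaire.
- In section 7.2, within the same 16 interviews, aim for about 4 with participants who attended only one visit or did not return the forms, offered by phone. Make this a target and not a quota.
- If none can be recruited, state that the acceptability conclusions apply to completers only.

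The change is one of wording, with the same number of interviews and staff and no effect on the quantitative analysis. It costs about 4 completer interviews and thins the sex and time-since-transplant cells, and some of the patients approached will decline. Patients who decline enrolment or never attend a first visit would still not be interviewed.

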### 5.4 *Administration and timing of self-reported measures:*

We will collect and enter all patient-reported data electronically using Research Electronic Data Capture (REDCap). The REDCap Survey is a tool for building and managing online surveys. Vanderbilt University, in collaboration with a consortium of institutional partners, has developed this software and workflow methodology for electronic collection and management of research and clinical trial data. Our research team has extensive experience using REDCap and will create and design the surveys in a web browser, with institutional information technology support. The REDCap Survey system offers secure, HIPAA compliant, web-based

Sexual Dysfunction Intervention Post-Bone Marrow Transplant  
Protocol version 7/02-28-2017

applications that provide an intuitive interface for participants to enter data, with real-time validation rules at the time of entry.

Participants will use tablet computers to complete questionnaires in clinic. If any participants refuse or are unable to complete the questionnaires on the computer, they will be permitted to use hard-copy paper versions. Participants who do not have a regularly scheduled clinic visit will be provided with remote access to REDCap system or paper-based questionnaire for home administration. The research team will contact patients twice to remind them to complete and return the surveys. If study participants fail to complete the surveys within the expected time point, we will report the data as missing and document the reason for incompleteness. Table 1 details the schedule for administering the self-report measures. All participants will complete baseline evaluation within 72 hours of study enrollment. All participants will then have a second evaluation at 6 months (+/- 2 weeks).

| Table 1              | Baseline (within 72 hours of informed consent) | 6 months from enrollment (+/- 2 weeks) |
|-----------------------------|---|---|
| Participant Measures |   |   |
| Demographics                | X   |   |
| Male sexual function        | X   | X   |
| Female sexual function      | X   | X   |
| QOL (FACT-BMT)              | X   | X   |
| Depression/Anxiety (HADS)   | X   | X   |
| Depression (PHQ-9)          | X   | X   |

